7.3.3. Dispensing

It is the responsibility of the investigator to ensure that ipilimumab is only dispensed to study subjects. The ipilimumab must be dispensed only from official study sites by authorized personnel according to local regulations.

7.4. Drug Ordering and Accountability

7.4.1. Initial Orders

Following submission and approval of the required regulatory documents, a supply of ipilimumab may be ordered from the site's Pharmacy by completing a Drug Request Form. The first request may take place at site opening.

Ipilimumab vials (40 mL) are shipped in quantities of five. The initial order should be limited to 25 vials (5 cartons of 5 vials each). Allow 5 business days for shipment of drug from the receipt of the Drug Request Form by the Sponsor (or designated third party vendor). Drug is protocol specific, but not patient specific. All product will be shipped by courier in a temperature-controlled container. Shipments will be made from a third party vendor. There will be no weekend or holiday delivery of drugs.

It is possible that sites may have more than one ipilimumab clinical study ongoing at the same time. It is imperative that only product designated for this protocol number be used for this study.

7.4.2. Re-Supply

Drug re-supply request form should be submitted electronically or by fax to a Sponsor-designated third party vendor, at least 5 business days before the expected delivery date. Deliveries will be made Tuesday through Friday.

When assessing need for resupply, institutions should keep in mind the number of vials used per treatment dose, and that shipments may take 5 business days from the Sponsor designated third party vendor receipt of request. Drug is not patient specific. Be sure to check with your pharmacy regarding existing investigational stock to assure optimal use of drug on hand.

7.5. Ipilimumab Accountability

It is the responsibility of the investigator to ensure that a current record of ipilimumab disposition is maintained at each study site where ipilimumab is inventoried and disposed. Records or logs must comply with applicable regulations and guidelines, and should include: Amount received and placed in storage area.

- Amount currently in storage area.
- Label ID number or batch number and use date or expiry date.
- Dates and initials of person responsible for each ipilimumab inventory entry/movement.
- Amount dispensed to and returned by each subject, including unique subject identifiers.
- Amount transferred to another area/site for dispensing or storage.
- Non-study disposition (e.g., lost, wasted, broken).
- Amount destroyed at study site.

7.6. Ipilimumab Destruction

If ipilimumab is to be destroyed on site, it is the investigator's responsibility to ensure that arrangements have been made for disposal and that procedures for proper disposal have been established according to applicable regulations, guidelines, and institutional procedures. Appropriate records of the disposal must be maintained. Provide a certificate of destruction to the Sponsor upon disposal.

8. ADVERSE EVENT REPORTING

8.1. Collection of Safety Information

An *Adverse Event (AE)* is defined as any new untoward medical occurrence or worsening of a pre-existing medical condition in a patient or clinical investigation subject administered an investigational (medicinal) product and that does not necessarily have a causal relationship with this treatment. An AE can therefore be any unfavorable and unintended sign (including an abnormal laboratory finding, for example), symptom, or disease temporally associated with the use of investigational product, whether or not considered related to the investigational product.

Adverse events can be spontaneously reported or elicited during open-ended questioning, examination, or evaluation of a subject. (In order to prevent reporting bias, subjects should not be questioned regarding the specific occurrence of one or more AEs.)

8.1.1. Serious Adverse Events

A *serious AE (SAE)* is any untoward medical occurrence that at any dose:

- results in death
- is life-threatening (defined as an event in which the subject was at risk of death at the time of the event; it does not refer to an event which hypothetically might have caused death if it were more severe)
- requires inpatient hospitalization or causes prolongation of existing hospitalization (see **NOTE** below)
- results in persistent or significant disability/incapacity
- is a congenital anomaly/birth defect
- is an important medical event (defined as a medical event(s) that may not be immediately life-threatening or result in death or hospitalization but, based upon appropriate medical and scientific judgment, may jeopardize the subject or may require intervention [eg, medical, surgical] to prevent one of the other serious outcomes listed in the definition above.) Examples of such events include, but are not limited to, intensive treatment in an emergency room or at home for allergic bronchospasm; blood dyscrasias or convulsions that do not result in hospitalization.)
- Suspected transmission of an infectious agent (eg, any organism, virus or infectious particle, pathogenic or non-pathogenic) via the study drug is an SAE.

Although pregnancy, overdose, cancer are not always serious by regulatory definition, these events must be handled as SAEs. (See Section 8.4 for reporting pregnancies.)

NOTE: The following hospitalizations are not considered SAEs:

- a visit to the emergency room or other hospital department lasting less than 24 hours that does not result in admission (unless considered an "important medical event" or a life-threatening event)

- elective surgery planned before signing consent
- admissions as per protocol for a planned medical/surgical procedure
- routine health assessment requiring admission for baseline/trending of health status (eg, routine colonoscopy)
- medical/surgical admission for purpose other than remedying ill health state that was planned before study entry. Appropriate documentation is required in these cases.
- Admission encountered for another life circumstance that carries no bearing on health status and requires no medical/surgical intervention (eg, lack of housing, economic inadequacy, caregiver respite, family circumstances, administrative).

8.1.2. Nonserious Adverse Events

A *nonserious adverse event* is an AE not classified as serious.

8.2. Assignment of Adverse Event Intensity and Relationship to Investigational Product

All adverse events, including those that are serious, will be graded according to the National Cancer Institute Common Terminology Criteria for Adverse Events (NCI CTCAE), Version 4.0.

The following categories and definitions of causal relationship to investigational product as determined by a physician should be used:

- **Related:** There is a reasonable causal relationship to investigational product administration and the adverse event.
- **Not Related:** There is not a reasonable causal relationship to investigational product administration and the adverse event.

The expression “reasonable causal relationship” is meant to convey in general that there are facts (eg, evidence such as de-challenge/re-challenge) or other arguments to suggest a positive causal relationship.

8.3. Collection and Reporting

Adverse events can be spontaneously reported or elicited during open-ended questioning, examination, or evaluation of a subject. (In order to prevent reporting bias, subjects should not be questioned regarding the specific occurrence of one or more AEs.)

If known, the diagnosis of the underlying illness or disorder should be recorded, rather than its individual symptoms. The following information should be captured for all AEs: onset, duration, intensity, seriousness, relationship to investigational product, action taken, and treatment required. If treatment for the AE was administered, it should be recorded in the medical record.

The investigator shall supply the sponsor and Ethics Committee with any additional requested information, notably for reported deaths of subjects.

8.3.1. Serious Adverse Events

The following information is provided to investigators for either inclusion in protocol documents or other related study documents. It will also be contained in the Study Agreement:

Following the subject’s written consent to participate in the study, all SAEs must be collected, including those thought to be associated with protocol-specified procedures. All SAEs must be collected that occur

within 90 days of discontinuation of dosing of the investigational product. If applicable, SAEs must be collected that relate to any later protocol-specified procedure (eg, a follow-up skin biopsy). The investigator should notify the Sponsor of any SAE occurring after this time period that is believed to be related to the investigational product or protocol-specified procedure.

All SAEs whether related or unrelated to the ipilimumab, must be immediately reported to the Sponsor or delegated CRO (by the investigator or designee) within 24 hours of becoming aware of the event. If only limited information is initially available, follow-up reports are required. The original SAE form must be kept on file at the study site.

All SAEs should be immediately reported to CRO:

[REDACTED]

Suspected Unexpected Serious Adverse Reactions (SUSAR) will be reported by the study Sponsor to the relevant Authorities and into the Eudravigilance database. The Sponsor will be provided with a simultaneous copy of all adverse events filed with the Authorities.

Serious adverse events, whether related or unrelated to investigational product, must be recorded on the SAE page and reported expeditiously to the Sponsor (or designee) to comply with regulatory requirements. An SAE report should be completed for any event where doubt exists regarding its status of seriousness.

All SAEs must be immediately reported by confirmed facsimile transmission (fax) and mailing of the completed SAE page. In some instances where a facsimile machine is not available, overnight express mail may be used. If only limited information is initially available, follow-up reports are required. (Note: Follow-up SAE reports should include the same investigator term(s) initially reported.) In selected circumstances, the protocol may specify conditions that require additional telephone reporting.

If the investigator believes that an SAE is not related to the investigational product, but is potentially related to the conditions of the study (such as withdrawal of previous therapy, or a complication of a study procedure), the relationship should be specified in the narrative section of the SAE page.

If an ongoing SAE changes in its intensity or relationship to the investigational product, a follow-up SAE report should be sent immediately to the sponsor. As follow-up information becomes available it should be sent immediately using the same procedure used for transmitting the initial SAE report. All SAEs should be followed to resolution or stabilization.

8.3.2. Handling of Expedited Safety Reports

In accordance with local regulations, the Sponsor will notify investigators of all SAEs that are suspected (related to the investigational product) and unexpected (ie, not previously described in the SMPC). In the European Union (EU), an event meeting these criteria is termed a Suspected, Unexpected Serious Adverse Reaction (SUSAR). investigator notification of these events will be in the form of an expedited safety report (ESR).

Other important findings which may be reported by the sponsor as an ESR include: increased frequency of a clinically significant expected SAE, a SAE considered associated with study procedures that could modify the conduct of the study, lack of efficacy that poses significant hazard to study subjects, clinically significant safety finding from a nonclinical (eg, animal) study, important safety recommendations from a study data monitoring committee, or sponsor decision to end or temporarily halt a clinical study for safety reasons.

Upon receiving an ESR from the Sponsor, the investigator must review and retain the ESR with the SMPC. Where required by local regulations or when there is a central IRB/IEC for the study, the sponsor will submit the ESR to the appropriate IRB/IEC. The investigator and IRB/IEC will determine if the informed consent requires revision. The investigator should also comply with the IRB/IEC procedures for reporting any other safety information.

In addition, suspected serious adverse reactions (whether expected or unexpected) shall be reported by the Sponsor to the relevant competent health authorities in all concerned countries according to local regulations (either as expedited and/or in aggregate reports).

8.3.3. Nonserious Adverse Events

The collection of nonserious AE information should begin at initiation of investigational product. In general, the collection period will last for 30 days after the last treatment administration. The exceptions are the immune-related AEs that occur within 90 days of discontinuation of dosing of the investigational product, which should also be collected.

If an ongoing nonserious AE worsens in its intensity, or if its relationship to the investigational product changes, a new nonserious AE entry for the event should be completed.

Nonserious AEs should be followed to resolution or stabilization, or reported as SAEs if they become serious. Follow-up is also required for nonserious AEs that cause interruption or discontinuation of investigational product, or those that are present at the end of study participation. Subjects with nonserious AEs at study completion should receive post-treatment follow-up as appropriate.

All identified nonserious AEs must be recorded and described in the medical record.

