End of treatment visit (EOT) will take place 30 + 2 days after the last dose of ipilimumab. This visit will require a complete evaluation of patient's symptoms, Karnofsky/Barthel scores, physical exam (including weight, vital constants and neurological exam), lab tests, collection of AEs and of concomitant medication. If the disease was not evaluated before, EOT visit should include a body and cranial CTscan/MRI.

6.2.1.e Follow-up visits.

Per protocol, the disease should be evaluated until death or confirmed progression (mWHO/immune response criteria). Tumor assessment will be performed with CT/MRI of brain, chest, abdomen and pelvis at baseline, at weeks 12 and 17 \pm 1 and then, every 9 \pm 1 weeks. The same method of assessment (CT or MRI) should be used throughout the patient's time on study for consistent evaluation of response.

After EOT visit, the occurrence of new SAEs and irAEs will be reported up to 90 days after last ipilimumab administration. Ongoing SAEs/irAEs will be followed up until recovery.

Survival status will be checked at week 12, 16-18 and then, every 8-10 weeks.

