6.3.2. Safety Assessments

All patients who receive at least one dose of ipilimumab will be considered evaluable for safety parameters. Additionally, any occurrence of non-SAE or SAE from time of consent forward, up to and including follow-up visits, will be reported. See Section 8: Adverse Event Reporting.

Safety will be evaluated for all treated patients using the National Cancer Institute (NCI) Common Terminology Criteria for Adverse Events (CTCAE), Version 4.0 (<http://ctep.cancer.gov>). Safety assessments will be based on medical review of adverse event reports and the results of vital sign measurements, physical examinations, and clinical laboratory tests.

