9.4.3 Safety Analyses

Descriptive statistics of safety will be presented for all treated subjects using the National Cancer Institute (NCI) Common Terminology Criteria for Adverse Events (CTCAE) version 4.0. All on-study AEs, drug-related AEs, immune-related AEs, SAEs, and drug-related SAEs will be tabulated using worst grade

per NCI CTCAE v4.0 criteria by system organ class and by preferred term. The listings by subject will be produced for all deaths, all SAEs, and all AEs leading to discontinuation of study drug. On-study laboratory parameters, including hematology, serum chemistry, liver function, and renal function will be summarized using worst grade per NCI CTCAE v4.0 criteria. The reporting period for safety data will be from the first dose of study medication to 90 days (> 5 half lives) after the last dose is received.

Immune-related Adverse Events (irAEs)

Immune-related adverse events (irAEs) are AEs of unknown etiology, which are consistent with an immune phenomenon and identified by the investigator as study treatment related. The irAEs will be defined using a predefined list of MedDRA highlevel group terms, high-level terms and preferred terms; changes may be made to this list with each new version of MedDRA. Six (6) subcategories of irAEs will be reported: GI, liver, skin, endocrine, neurological, and other. Immune-related AE summaries will also be produced on diarrhea as a separate grouped term. Analysis of irAEs will be based on all treated subjects who received at least one dose of study therapy, and the reporting period will be from the first dose of after the last dose is received.

Immune-mediated Adverse Reactions (imARs)

This study will also describe immune-mediated adverse reactions (imARs) using the same adjudication algorithm and predefined list of AEs of special interest (enterocolitis, hepatitis, dermatitis, endocrinopathies, neuropathies, and other) used for the USPI. Specifically, the determination of imAR will take into account available clinical evidence through ruling out non-inflammatory etiologies such as infection or tumor progression, and consideration of evidence of inflammation such as tumor biopsies or responsiveness to steroids, but not the causality assessment of the investigator. imARs are likely to be

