inflammatory events associated with ipilimumab treatment. Documentation of surveillance, intervention and outcomes are to be documented in the CRFs for inclusion of the imAR assessment. Analysis of imARs will be based on all treated subjects who received at least one dose of ipilimumab. The reporting period will be from the first dose of study therapy to 90 days after the last dose is received.

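### Non-serious adverse events not classed as immune-related are collected to about 30 days after the last dose, but the safety tables that should contain them run to 90 days

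*Protocol*

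**What the plan says.** The protocol gives several collection rules and one reporting window.

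- **Non-serious AEs, Section 8.3.3.** Collection starts with study drug. "In general, the collection period will last for 30 days after the last treatment administration". The next sentence adds: "The exceptions are the immune-related AEs that occur within 90 days of discontinuation of dosing of the investigational product, which should also be collected".
- **Serious AEs, Section 8.3.1.** Collection runs from consent to 90 days after dosing stops.
- **Follow-up, Section 6.2.1.e.** "After EOT visit, the occurrence of new SAEs and irAEs will be reported up to 90 days after last ipilimumab administration". The end-of-treatment (EOT) visit falls about 30 days after the last dose, and no other class of new event is named after it.
- **Safety assessments, Section 6.3.2.** "any occurrence of non-SAE or SAE from time of consent forward, up to and including follow-up visits, will be reported". The paragraph then refers the reader to Section 8. Table 12 likewise shows AE and SAE recording for the whole study.
- **Analysis, Section 9.4.3.** The tables cover all on-study AEs, drug-related AEs, immune-related AEs (irAEs), SAEs and drug-related SAEs. "The reporting period for safety data will be from the first dose of study medication to 90 days" after the last dose. For imARs: "The reporting period will be from the first dose of study therapy to 90 days after the last dose is received". The imAR determination uses clinical evidence "but not the causality assessment of the investigator".
- **SAP.** Section 1.6 tabulates treatment-related toxicity and Section 1.7 all AEs. Neither states a time window. Section 1.9 uses 30 days after the last dose, for deaths only.

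**The concern.** A safety table should not claim a period for which the data were not collected. An all-AE table labelled as running to 90 days will be read as showing that little happened between days 31 and 90. Under Section 8.3.3, ordinary non-serious events in that period were simply not sought. Sites that follow Section 6.3.2 or Table 12 instead may record them, so completeness could differ between sites.

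This matters more than usual here. Section 1.4 says the safety of ipilimumab with whole-brain radiotherapy has not been described, and AE rates are a secondary objective (Section 2.2). Non-serious events caused by radiotherapy are not immune-related, so the 90-day exception does not cover them.

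The imAR analysis adds a second difficulty. It is meant to be independent of the site's causality judgement, but after day 30 that judgement helps decide which non-serious events enter the AE data.

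**Working it through.** **Inputs.** Four doses every 3 weeks (Section 5.1.1); collection to 30 days (8.3.3); reporting to 90 days (9.4.3); terminal half-life 14.7 days, or 297 to 414 hours from the earlier study (1.3.3.b).

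**The plan's own figure.** Section 9.4.3 says 90 days exceeds five half-lives. 90 / 14.7 = 6.1, and 5 × 14.7 = 73.5 days. With 297 to 414 hours (12.4 to 17.25 days), 90 days is 7.3 to 5.2 half-lives. The statement reproduces. The 30-day limit is 30 / 14.7 = 2.0 half-lives.

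**Gap by event class, if Section 8.3.3 governs.**

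| Class | Collected to | Reported to | Gap |
|---|---|---|---|
| SAEs | 90 days | 90 days | 0 |
| Non-serious, classed as immune-related | 90 days | 90 days | 0 |
| Non-serious, not so classed | 30 days | 90 days | 60 days |

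If Section 6.3.2 or Table 12 governs instead, the third row also has no gap.

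**Share of the window.** With the first dose on day 1, dose k falls on day 1 + 21(k − 1). Collection ends 30 days after the last dose, and the window ends 90 days after it.

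| Doses received | Last dose | Collection ends | Window ends | Uncollected days | Share |
|---|---|---|---|---|---|
| 4 | day 64 | day 94 | day 154 | 95–154 | 60/154 = 39% |
| 3 | day 43 | day 73 | day 133 | 74–133 | 60/133 = 45% |
| 2 | day 22 | day 52 | day 112 | 53–112 | 60/112 = 54% |
| 1 | day 1 | day 31 | day 91 | 32–91 | 60/91 = 66% |

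In elapsed days (153 after four doses, 90 after one) the shares are 39% and 67%. The table takes the last treatment in 8.3.3 to be the last ipilimumab dose, as 6.2.1.e does. If a later radiotherapy fraction counted, the gap would be shorter for patients who stop ipilimumab early.

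**From time to events.** The documents give no late event rate. As an illustration only, let the rate on days 31–90 be r times the earlier rate, with rare events. The missed share of this class is then 60r / (93 + 60r) after four doses and 60r / (30 + 60r) after one. For r = 0.1 to 1 this gives 6% to 39% and 17% to 67%. The range follows from the assumed r and is not an estimate for this trial.

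**The imAR route.** Section 9.4.3 defines irAEs partly by the investigator's attribution to study treatment. Section 5.1.6 widens capture, because suspected immune-related reactions must also go on an AE or SAE form. So on days 31–90 a non-serious event enters the AE data if the site classes or suspects it as immune-related. One attributed to the brain metastases or to radiotherapy does not, and cannot then be adjudicated from the AE data. Sections 1.3.4 and 5.1.10 note that immune endocrinopathy can resemble brain metastasis, which every patient here has.

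**The case against.** The strongest reply is that the protocol runs a deliberate tiered scheme. Sections 6.2.1.e, 8.3.1 and 8.3.3 agree on 30 days for ordinary AEs and 90 days for SAEs and irAEs, the events most relevant to ipilimumab. Other provisions soften the gap further:

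- Section 8.3.3 requires identified non-serious AEs to be described in the medical record.
- Section 5.1.10 presumes dermatitis and endocrinopathy to be immune-mediated unless another cause is found.
- Section 6.4.1.e repeats haematology and chemistry 90 days after the last dose, whatever the causality label.
- Section 9.4.3 asks for surveillance, intervention and outcome in the CRFs for the imAR assessment.
- Immune-related events are said to start commonly 3 to 10 weeks after the first dose, about days 21 to 70, before collection ends on day 94 of a full course.

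Most of this stands and limits the point. The tiered scheme is defensible in itself; the fault is that the reporting window for all AEs does not follow it. Section 6.3.2 and Table 12 do not cure this, because 6.3.2 sends the reader back to Section 8, where the 30-day rule is. A note in the medical record is not an entry in the trial data. The onset argument is weaker for shortened courses: after one or two doses the uncollected days overlap days 21 to 70, and in the phase 3 trial described in Section 1.3.5.b only 61% of those randomised to ipilimumab arms received all four doses. Even so, the overlap matters only for events the site does not recognise as immune-related.

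**Conclusion.** The point holds in a limited form. For non-serious AEs not classed as immune-related, the stated analysis window is 60 days longer than the collection rule in 8.3.3 and 6.2.1.e supports, and other sections contradict that rule. This assumes that sites follow 8.3.3. The 39% after four doses measures time, not missed events.

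A reader might go further in four ways that the documents do not support:

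- **All safety rates are necessarily understated.** SAEs and recognised irAEs are collected to 90 days, and under 6.3.2 or Table 12 nothing in the window is lost.
- **The data for imAR adjudication do not exist.** Suspected immune-related reactions, SAEs and 90-day laboratory results are all captured.
- **The imAR method fails altogether.** Only late non-serious events that the site neither classes nor suspects as immune-related can escape it.
- **The SAP reports only treatment-related toxicity.** SAP Section 1.7 and Annex II cover all AEs.

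The SAP text available has no tables for the irAE categories or imARs promised in protocol 9.4.3. That is a separate, minor completeness point and does not bear on the collection window.

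**What to change.** Choose one window and use it in Sections 6.2.1.e, 6.3.2, 8.3.3, 9.4.3 and Table 12.

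1. **Preferred:** collect all AEs from first dose to 90 days after the last dose, keeping SAE collection from consent. The extra work is small: asking about and recording AEs around the 90-day laboratory tests already scheduled in Section 6.4.1.e. Table 12 has no column for that time point and would need one.
2. **Otherwise:** keep the tiered scheme, limit the all-AE and drug-related AE tables to 30 days after the last dose, and say so in 9.4.3. Keep 90 days for SAEs and irAEs. State that non-serious imARs after day 30 are ascertained only among events the site classed or suspected as immune-related. This costs only wording.

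In either case, put the chosen window in the titles or footnotes of the tables in SAP Sections 1.6 to 1.8 and the two annexes.
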